A RANDOMIZED, VEHICLE-CONTROLLED, SAFETY AND EFFICACY STUDY OF EVO101 IN ADULT SUBJECTS WITH ATOPIC DERMATITIS

Protocol Number	EVO101-AD001
Protocol Final Date	20 April 2022
Amendment 1 Date	10 June 2022
Amendment 2 Date	06 January 2023
Amendment 3 Date	11 May 2023
Study Drug	EVO101 Topical Cream, 0.1%
IND Number	155054
Sponsor	Evommune, Inc. [name]

CONFIDENTIAL INFORMATION

The information contained herein is confidential and the proprietary property of Evommune. Any use or disclosure of such information without the prior written authorization of Evommune is expressly prohibited.

PROTOCOL AMENDMENT 3.0 SUMMARY OF CHANGES

Changes to the protocol, introduced in Amendment 3.0, are summarized in the following table.

Section(s)	Modification	Rationale
Synopsis	Comparisons between active and vehicle treated arms will be conducted using a one-sided test instead of a two- sided test.	For consistency between the protocol and Statistical Analysis Plan (SAP)
15.1, 15.4, 15.8	Comparisons between active and vehicle treated arms will be conducted using a one-sided test instead of a two- sided test.	For consistency between the protocol and SAP

PROTOCOL AMENDMENT 2.0 SUMMARY OF CHANGES

Changes to the protocol, introduced in Amendment 2.0, are summarized in the following table.

Section	Modification	Rationale
Title Page	Updated Sponsor Address	New headquarters established for Evommune (Sponsor)
6	Updated Schedule of Assessments	For consistency between Table 3 and Section 13.1.4.1
13.1.4.1	Provided additional direction on recording local skin responses as adverse events where appropriate	Clarification for study sites
15.2	Removed "and received study drug" from the intent-to-treat (ITT) population definition	For consistency between the protocol and Statistical Analysis Plan (SAP)
15.5.1	Removed "and received study drug" from the ITT population definition	For consistency between the protocol and SAP

PROTOCOL AMENDMENT 1.0 SUMMARY OF CHANGES

Changes to the protocol, introduced in Amendment 1.0, are summarized in the following table.

Section	Modification	Rationale
1.1	Updated description of inhibitory properties of EVO101, primarily as an inhibitor of interleukin 1 receptor- associated kinase 4; removed characterization as an inhibitor of tropomyosin receptor kinase A (TrkA)	For a more accurate characterization of the primary pharmacology of EVO101

I have read and understand all study related information provided to me.

The objectives and conduct of this protocol as well as the results deriving from this study will be treated confidentially and will not be made available to third parties without prior authorization by Evommune. All rights of publication of the results reside with Evommune unless other agreements were made in a separate contract.

Investigator's Signature

Date

Investigator's Name (print)

PROCEDURES IN CASE OF EMERGENCY

Table 1: Emergency Contact Information

Role in Study	Name	Telephone Number/email	
Responsible Physician			
24-hour emergency contact			

SYNOPSIS

Name of Sponsor/Company: Ev	ommune, Inc.	
Name of Investigational Product: EVO101 Topical Cream, 0.1%		
Protocol Number: EVO101-AD001	Phase: 2a	Country: USA
Title of Study: A RANDOMIZED OF EVO101 IN ADULT SUBJEC	D, VEHICLE-CONTROLLED, S. CTS WITH ATOPIC DERMATIT	AFETY AND EFFICACY STUDY IS
Objectives: Primary: Assess the safety, tolera applied twice daily in adults with Secondary: The secondary object Topical Cream 0.1%, applied twice Study Design: Randomized, Dou	ability, and preliminary efficacy of atopic dermatitis (AD). tive of this study will be to assess be daily in adults with AD. ble-Blind, Parallel Group, Vehicle	f EVO101 Topical Cream, 0.1%, the pharmacokinetics of EVO101
Number of subjects (planned): 1	118	
Diagnosis and main criteria for	inclusion: Adults with mild to me	oderate AD
Investigational product, dosage, a day (BID)	, and mode of administration: E	VO101 Topical Cream, 0.1% twice
Duration of treatment: 8 weeks		
Reference therapy, dosage, and	mode of administration: EVO10	11 Topical Cream, Vehicle BID
Criteria for evaluation:		
Efficacy: Investigator Global Assessment (IGA), Eczema Area and Severity Index (EASI), Body Surface Area (BSA), Pruritus-Numerical Rating Scale (NRS)		
Safety: Adverse Event (AEs), Local Skin Response (LSRs), Physical Exam, Serum Chemistry, Hematology and Urinalysis, ECG		
Pharmacokinetics: Plasma drug	concentrations	
Statistical methods:		
Sample size justification:		
The assumed true standard deviati score is 50%. Based on the use of sample size of 118 subjects (59 su a mean between-group difference	ion of the percentage change from a one-sided test at the alpha=0.05 bjects/treatment arm) will provide of 30 percentage points.	Baseline to Week 8 in the EASI level of significance, a total e greater than 90% power to detect
Primary efficacy analysis:		
The primary efficacy analysis will be conducted in the intent-to-treat population (all randomized subject) using an analysis of variance (ANOVA) model with the percentage change from Baseline to Week 8 in EASI as the dependent variable and treatment group and the randomization stratification variable as factors. The two arms will be compared using a one-sided test at the alpha=0.05 level of significance.		
Secondary efficacy analyses:		
All secondary endpoints defined as the percentage change from Baseline will be analyzed using the same type of ANOVA model as specified for the primary analysis. All change from Baseline		

secondary endpoints will be analyzed using analysis of covariance (ANCOVA) models with treatment group and the randomization stratification variable as factors and with the baseline value of the corresponding endpoint as a covariate. Secondary endpoints that are defined as proportion variables will be analyzed using Pearson's chi-square test or (if more than 25% of expected cell frequencies are less than 5) Fisher's exact test. All secondary analyses will be conducted using one-sided tests at the alpha=0.05 level of significance, with no adjustments for multiplicity.

TABLE OF CONTENTS

PROTO	OCOL AMENDMENT 3.0 SUMMARY OF CHANGES	2
PROTO	OCOL AMENDMENT 2.0 SUMMARY OF CHANGES	3
PROTO	OCOL AMENDMENT 1.0 SUMMARY OF CHANGES	4
SPONS	SOR SIGNATURE PAGE	5
INVES	STIGATOR SIGNATURE PAGE	6
PROCE	EDURES IN CASE OF EMERGENCY	7
SYNOI	PSIS	8
1.	INTRODUCTION	16
1.3.	Study Rationale	21
2.	STUDY OBJECTIVES	
2.1.	Primary Objective	
2.2.	Secondary Objectives	
3.	STUDY ENDPOINTS	23
3.1.	Efficacy Endpoints	23
3.2.	Pharmacokinetic Endpoints	
4.	INVESTIGATIONAL PLAN	
4.1.	Overall Study Design	
4.2.	Study Population and Number of Subjects	
4.3.	Duration of the Study	
5.	STUDY DESIGN SCHEMATIC	25
6.	SCHEDULE OF ASSESSMENTS	
7.	SELECTION OF SUBJECTS	
7.1.	Inclusion Criteria	
7.2.	Exclusion Criteria	

8.	STUDY DRUG	29
8.1.	Description of Study Drug	29
8.2.	Study Drug Packaging and Labelling	29
8.3.	Study Drug Storage	29
8.4.	Randomization and Blinding	29
8.5.	Study Drug Administration and Application	29
8.6.	Study Drug Dispensing and Return	30
8.7.	Study Drug Compliance	30
8.8.	Study Drug Accountability and Disposal	30
9.	CONCOMITANT MEDICATIONS AND PROCEDURES	31
9.1.	Permitted Treatments and Procedures	31
9.2.	Prohibited Treatments and Procedures	31
10.	STUDY PROCEDURES BY VISIT	32
10.1.	Screening Period	32
10.2.	Baseline (Day 1)	32
10.3.	Week 2	33

Table 6:	Investigator Assessed Local Skin Reactions	40

LIST OF FIGURES

Figure 1: IRAK4 Functions Downstream of TLR and IL-1 Family Cytokine Receptors......17

LIST OF ABBREVIATIONS

The abbreviations listed below are a non-exhaustive list of those commonly used in Evommune, Inc., study documents. Not all acronyms listed below are used within this document.

Abbreviation or Specialist Term	Explanation
AE	Adverse event
AD	atopic dermatitis
AUC ₀₋₂₄	area under the plasma concentration-time curve over the last 24-h dosing interval
BID	twice a day
BSA	body surface area
С	Celsius
CFR	code of federal regulations
CNS	central nervous system
eCRF	electronic case report form
CRO	clinical research organization
C _{max}	maximum plasma concentration
СҮР	cytochrome P450
DNA	deoxyribonucleic acid
DNCB	dinitrochlorobenzene
DP	drug product
DRF	dose range-finding
DS	drug substance
EASI	eczema area and severity index
ECG	electrocardiogram
eCRF	electronic case report form
FDA	Food and Drug Administration
GCP	good clinical practices
GLP	good laboratory practices
HED	human equivalent dose
ICF	informed consent form
ICH	International Council for Harmonization of Technical Requirements for Pharmaceuticals for Human Use
IEC	International ethics committee
IGA	investigator global assessment
IL	interleukins

Abbreviation or Specialist Term	Explanation
IND	Investigational New Drug
IR	infrared (spectrophotometry)
IRAK4	interleukin 1 receptor associated kinase 4
IRB	institutional review board
ITT	intent-to-treat
IWRS	interactive web-based randomization system
kg	kilogram
LSR	local skin response
MedDRA	medical dictionary for regulatory activities
mg	milligram
mL	milliliter
mmHg	millimeters of mercury
MyD88	myeloid differentiation primary response gene 88
NF-kB	nuclear factor-kappa B
ng	nanograms
NGF	nerve growth factor
NOAEL	no-observed-adverse-event-level
NRS	numerical rating scale
РК	pharmacokinetics
ppm	parts per million
PI	principal investigator
RBC	red blood cell
SAE	serious adverse event(s)
SD	standard deviation
Th	T helper type
TLR	toll-like receptor
TEAE	treatment emergent adverse event
TRPV1	Transient Receptor Membrane Potential cation channel subfamily V member 1
US	United States
VEGF	vascular endothelial growth factor

Evommune, Inc. EVO101 Topical Cream

1. INTRODUCTION

1.1.			

EVO101-AD001

1.3. Study Rationale

Study EVO101-AD001 is planned as a randomized, double-blinded, parallel group proof-ofconcept trial in which safety, preliminary efficacy and pharmacokinetics will be assessed. Approximately 118 adult subjects with mild-to-moderate AD will be randomized and apply study drug or vehicle to their affected areas twice daily for 8 weeks. This dosing regimen has been selected because it was found to be well-tolerated in a previous study, EVO101-HV001, conducted in adult healthy volunteers.

2. STUDY OBJECTIVES

2.1. Primary Objective

The primary objective of this study will be to assess the safety, tolerability, and preliminary efficacy of EVO101 Topical Cream, 0.1%, applied twice daily, in adults with AD.

2.2. Secondary Objectives

The secondary objective of this study will be to assess the pharmacokinetics of EVO101 Topical Cream, 0.1%, applied twice daily, in adults with AD.

3. STUDY ENDPOINTS

3.1. Efficacy Endpoints

The primary efficacy endpoint for this trial will be:

• Mean percentage change from Baseline in EASI score at Week 8

Secondary efficacy endpoints for this study will be:

- IGA response (≥2 point change from baseline) at Week 8
- Change from Baseline in IGA at Week 8
- Mean change from Baseline in BSA affected at Week 8

Exploratory efficacy endpoints for this study will be:

- EASI-75 and EASI-90 from Baseline to Week 2, 4 and 8
- Mean change from Baseline in EASI at Weeks 2 and 4
- Proportion of subjects achieving an IGA score of 0 to 1 who have an improvement of ≥ 2 points from Baseline at Week 8
- Change from Baseline in IGA score at Weeks 2, 4 and 8
- Mean change from Baseline in the pruritus-NRS score at Weeks, 2, 4 and 8
- Mean and percentage change from Baseline in the pruritus-NRS score at Week 8
- Proportion of subjects achieving a 4-point improvement in the pruritus-NRS score from Baseline to Week 8
- Mean change from Baseline in BSA affected at Weeks, 2, 4 and 8

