7. SELECTION OF SUBJECTS

Subject selection criteria are outlined below. Any questions on the eligibility of a subject for this study must be referred to the Sponsor or their designee, prior to enrollment. No exceptions to inclusion or exclusion criteria will be made.

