7.1. Inclusion Criteria

Subjects must meet all of the following criteria to be eligible for study participation:

- 1. Signed informed consent.
- 2. Willing and able to comply with the study visit schedule, procedures, and questionnaires.
- 3. Male or non-pregnant, non-lactating, females, age ≥ 18 years.
- 4. Chronic AD (according to the American Academy of Dermatology Consensus Criteria) that has been present for ≥1 year before the Screening visit.
- 5. Investigator's Global Assessment score of 2 to 3 at Screening and Baseline.
- 6. EASI of 5-20 at screening and baseline.
- 7. BSA of AD involvement, excluding the face and intertriginous areas, of 4% to 12% at Screening and Baseline.
- 8. Application of a stable dose of non-medicated topical moisturizer twice daily for \geq 7 days prior to the Baseline visit and willing to maintain stable dosing during study participation
- 9. Completed electronic diary entries for pruritus for a minimum of 4 of 7 days preceding randomization at the Baseline visit.
- 10. Willing to use effective contraceptive method, if applicable, during study participation and for 30 days following the end of treatment.

For women of childbearing potential: agree to remain abstinent (refrain from heterosexual intercourse) or use a highly effective contraceptive method during the treatment period and for at least 30 days after the last application of study drug.

A woman of childbearing potential is defined as a postmenarcheal female, who has not reached a postmenopausal state (≥ 12 continuous months of amenorrhea with no identified cause other than menopause) and has not undergone surgical sterilization (removal of ovaries and/or uterus).

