8.4. Randomization and Blinding

The Sponsor, the clinical research organization (CRO), the Investigator, study site personnel and subjects will be blinded to treatment assignment.

The integrity of this clinical study must be maintained by observing the treatment blind. If an AE occurs which cannot be managed without knowing whether the subject is receiving active study drug or vehicle solution, the Interactive Web-based Randomization System (IWRS) system will be used to obtain treatment assignment information. The Medical Monitor must be notified whenever study medication is unblinded, preferably prior to unblinding a subject.

At the Baseline visit, qualified subjects will be randomized to treatment using an IWRS. The IWRS will assign a study drug kit number. The kit number will be recorded in the electronic case report form (eCRF).

Approximately 118 subjects will be randomized in a 1:1 ratio to active treatment or vehicle treatment. The randomization will be stratified by baseline IGA score (IGA 2, IGA 3). At most 40% of randomized subjects can be in the IGA 2 stratum.

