15.4.2. Secondary Efficacy Analyses

All secondary endpoints defined as the percentage change from baseline will be analyzed using the same type of ANOVA model as specified for the primary analysis. All change from baseline secondary endpoints will be analyzed using analysis of covariance (ANCOVA) models with treatment group and the randomization stratification variable as factors and with the baseline value of the corresponding endpoint as a covariate. Secondary endpoints that are defined as proportion variables will be analyzed using Pearson's chi-square test or (if more than 25% of expected cell frequencies are less than 5) Fisher's exact test. All secondary analyses will be conducted using one-sided tests at the alpha=0.05 level of significance, with no adjustments for multiplicity.

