8.3.6 Secondary and Exploratory Analyses

Protocol title: A RANDOMIZED, VEHICLE-CONTROLLED, SAFETY AND EFFICACY STUDY OF EVO101 IN ADULT SUBJECTS WITH ATOPIC DERMATITIS

Sponsor code: EVO101-AD001

code: EPQ1001

Version number: Final 1.0

Date: 17-AUG-2023

Derivations of the following assessments are described in appendix 10.1.

The following summaries and analyses will be conducted:

EASI:

- Summary statistics at baseline, Week 2, Week 4 and Week 8 will be provided by each treatment group as well as for the change and percentage change from baseline. These analyses will also be conducted using the PP population.
- Number and percentage of subjects with EASI-75 at Week 2, Week 4 and Week 8 (defined as a subject with a percentage change from baseline <= - 75). These analyses will also be conducted using the PP population.
- Number and percentage of subjects with EASI-90 at Week 2, Week 4 and Week 8 (defined as a subject with a percentage change from baseline <= - 90).
- A listing with the visit, date of the assessment, score, change and percentage from baseline and the flags of EASI-75 and EASI-90.

IGA:

- Summary statistics at baseline, Week 2, Week 4 and Week 8 will be provided by each treatment group.
- Number and percentage of subjects with IGA response (≥2 points change from baseline (i.e., a change from baseline ≤ -2) at Week 8 and comparisons between treatments will be conducted in the ITT and PP populations.
- Number and percentage of subjects with IGA success (subjects with a score of 0 to 1 who have an improvement of ≥ 2 points, that means a change from baseline ≤ -2) from Baseline at Week 8 and comparison between treatments.
- A listing with the visit, date of the assessment, score, change from baseline and the flags of IGA response and IGA score of 0 to 1 who have an improvement of ≥ 2 points achievement.

BSA:

- Summary statistics at baseline, Week 2, Week 4 and Week 8 will be provided by each treatment group as well as for the change and the percentage change from baseline.
- Comparison between treatments for the change and percentage change from baseline to each visit.
- A listing with the visit, date of the assessment, value, change and percentage change from baseline.

Pruritus-NRS:

• For the assessment of pruritus-NRS:

Protocol title: A RANDOMIZED, VEHICLE-CONTROLLED, SAFETY AND EFFICACY STUDY OF EVO101 IN ADULT SUBJECTS WITH ATOPIC DERMATITIS

Sponsor code: EVO101-AD001

code: EPQ1001

Version number: Final 1.0

Date: 17-AUG-2023

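### Do the duplicate IGA response endpoint and the doubled baseline IGA term in the IGA-change model call for a change to the plan?

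*Protocol*

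**What the plan says.** **Endpoints.** Protocol section 3.1 has the secondary endpoint "IGA response (≥2 point change from baseline) at Week 8" and the exploratory endpoint "Proportion of subjects achieving an IGA score of 0 to 1 who have an improvement of ≥ 2 points from Baseline at Week 8". SAP section 8.3.6 gives the direction of the first, "IGA response (≥2 points change from baseline (i.e., a change from baseline ≤ -2) at Week 8", and describes the second as "subjects with a score of 0 to 1 who have an improvement of ≥ 2 points, that means a change from baseline ≤ -2". It plans a treatment comparison for each.

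**Entry and stratification.** Protocol section 7.1 requires "Investigator's Global Assessment score of 2 to 3 at Screening and Baseline", and section 7 adds "No exceptions to inclusion or exclusion criteria will be made". Section 8.4 states "The randomization will be stratified by baseline IGA score (IGA 2, IGA 3"), with the IGA 2 stratum capped at 40%. No other stratification factor is named.

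**Model.** Protocol section 15.4.2 analyses every secondary endpoint defined as a change from baseline by ANCOVA "with treatment group and the randomization stratification variable as factors and with the baseline value of the corresponding endpoint as a covariate". Change in IGA at Week 8 is one of these endpoints. SAP section 8.6 refers the reader to 8.3.5 and 8.3.6 for the covariates, but the model text of 8.3.6 is not visible in the public copy.

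**The concern.** Two features of the design appear to collide with the analysis.

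First, a subject who starts at 2 or 3 and improves by at least 2 points must finish at 0 or 1. The extra condition in the exploratory endpoint then removes nobody. A report could show the same counts under two names, and a reader could take them for two pieces of support. Reaching clear or almost clear, whatever the point change, would not be tested as such.

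Second, baseline IGA takes only two values, and these are the randomization strata. A model with both the stratum factor and the baseline covariate contains the same information twice. If that made the model impossible to fit, a secondary endpoint would lack a usable analysis, and its replacement would have to be chosen after the fact.

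**Working it through.** The plan gives no figure on this point. Its one sample-size figure concerns EASI and is not involved. It does reproduce: 30/(50·√(2/59)) = 3.26, and 3.26 − 1.645 = 1.61, which gives power of about 0.947 against the stated figure of more than 90%.

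**1. Are the two binary endpoints the same?** Inputs: baseline IGA in {2, 3} (protocol 7.1), Week 8 IGA in {0, 1, 2, 3, 4} (protocol 11.1), and response as a change of −2 or lower (SAP 8.3.6). That gives 2 × 5 = 10 pairs.

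| Baseline IGA | Week 8 scores counted as response | Week 8 scores counted as success |
|---|---|---|
| 2 | 0 | 0 |
| 3 | 0, 1 | 0, 1 |

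The flags agree in 10 of 10 pairs. The 0-to-1 condition would matter only for a move from 4 to 2, and baseline 4 is ineligible. The protocol's wording gives no direction. Read literally it would count a worsening from 2 to 4 as a response, so agreement would be 9 of 10. The SAP closes that gap.

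**2. Is the IGA-change model singular?** Let s = 1 for stratum IGA 3 and s = 0 for stratum IGA 2. If the stratum matches baseline for everyone, baseline IGA = 2 + s. The columns (intercept, treatment, s, baseline) then satisfy 2·intercept + s − baseline = 0. There are 4 columns of rank 3, and the null vector is v = (2, 0, 1, −1).

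**3. What can still be estimated?** A contrast L is estimable when L·v = 0.

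- Treatment difference, L = (0, 1, 0, 0): L·v = 0, so it is estimable.
- Arm mean with stratum weight w on IGA 3 and the covariate at its mean b: L·v = 2 + w − b. At the cap, 40% of 118 is 47.2, so at most 47 subjects are at IGA 2 and 71 at IGA 3, giving b = 2 + 71/118 = 2.602. Equal weights (w = 0.5) give 2.5 − 2.602 = −0.102, which is not estimable. Observed weights (w = 71/118) give 0, which is estimable.

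**4. Does the treatment result move?** An illustrative simulated outcome for 118 subjects (47 at IGA 2, 71 at IGA 3) was fitted three ways.

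| IGA terms in model | Columns | Rank | Treatment estimate | SE | Residual df |
|---|---|---|---|---|---|
| Stratum only | 3 | 3 | −0.2062 | 0.1435 | 115 |
| Baseline only | 3 | 3 | −0.2062 | 0.1435 | 115 |
| Both | 4 | 3 | −0.2062 | 0.1435 | 115 |

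The residual df is 118 − 3 = 115 in every fit, because the fourth column adds no rank.

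**5. What if a few subjects are stratified wrongly?** The matrix then has full rank but is nearly collinear. With 1, 3 or 6 such subjects in the same data, the treatment SE was 0.1433, 0.1438 and 0.1438. The estimate moved by at most 0.2274 − 0.2062 = 0.0212, about 0.15 of an SE. Over 2,000 simulated runs with 3 mis-stratified subjects, the second IGA term raised the treatment SE by 0.4% on average and 1.4% at most. The variance inflation (near 10 with 3 subjects) falls on the two IGA coefficients, which nobody plans to interpret.

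**The case for a change.** The best case for acting is that both facts are certain under the stated definitions and the remedy is only wording. Entering baseline IGA once, and deleting or relabelling the duplicate endpoint, would need no new data and would leave sample size alone. Settled before unblinding, it would spare the analyst a choice later. Adjusted arm means could come back blank under equal stratum weights. With no multiplicity adjustment, readers must judge for themselves how many separate results support efficacy. An endpoint of IGA 0 or 1 without the 2-point condition would add something, since it differs for subjects who move from 2 to 1, and up to 40% may start at 2.

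The facts stand; the consequences mostly do not.

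- The model can be fitted. Software that uses a generalized inverse, or drops the aliased column, returns the same treatment comparison as the reduced model, so the analyst's choice affects nothing that is tested.
- No visible passage requests equal-weight adjusted arm means for IGA, and observed-margin means are available from the same model.
- The SAP's version history shows that 8.3.6 received its own procedure for change in IGA under multiple imputation. With that text not visible, nobody can say that the SAP repeats the duplication.
- The duplicate endpoint is labelled exploratory, and the same comparison on the same flag gives the same answer. The exploratory list also repeats Week 8 change in IGA and in BSA from the secondary list, so overlap is already plain to a reader.
- Dropping the 2-point condition changes what counts as success: a 1-point gain from IGA 2 would qualify. Nothing in the documents shows that to be better. Since IGA is summarised at each visit and listed by subject, moves from 2 to 1 can be seen in any case.

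**Conclusion.** The observations hold but call for no change. With baseline IGA limited to 2 or 3 and the SAP's directional definition, the secondary response and the exploratory success endpoints at Week 8 are one variable. Protocol 15.4.2 read literally states one covariate too many for change in IGA. The effect on the treatment difference, its standard error and its degrees of freedom is nil when stratum and baseline agree. With 3 mis-stratified subjects the standard error rises by about 0.4%. The primary EASI analysis, the BSA model, sample size and power are untouched.

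This is a redundancy that an analyst resolves on sight by letting one of two identical terms drop out, and a duplicate exploratory line that costs no alpha. Removing either would alter no treatment result or conclusion. The one substantive alternative, IGA 0 or 1 alone, is a debatable choice of endpoint and does not correct an error.

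The conclusion assumes that eligibility is enforced, that the SAP's direction governs, and that IGA values stay within 0 to 4. An imputed value below 0 could separate the two flags, and the imputation text is not visible. It also assumes that the unseen part of SAP 8.3.6 does not call for equal-weight arm means from the two-term model.
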